3.4. Schedule of Assessments

Refer to the protocol for a full description of all study procedures and assessment schedules for this study.

4. DATA HANDLING DEFINITIONS AND CONVENTIONS

4.1. Scheduled Study Evaluations and Study Periods

4.1.1. Day 1

Day 1 is the date that the first dose of study drug (tafasitamab/placebo, lenalidomide, or rituximab) is administered to the participants.

For randomized participants not treated with any study drug, Day 1 is defined as the date of randomization.

4.1.2. Study Day

If a visit/reporting date is on or after Day 1, then the study day at the visit/reporting date will be calculated as

```
Day \# = (visit/reporting date - Day 1 date + 1).
```

If the visit/reporting date is before Day 1, then the study day at the visit/reporting date will be calculated as

```
Day \# = (visit/reporting date - Day 1 date).
```

A study day of -1 indicates 1 day before Day 1.

4.1.3. Baseline Value

Baseline is the last nonmissing measurement obtained before the first administration of tafasitamab/placebo, lenalidomide, or rituximab, unless otherwise defined.

For randomized participants not treated with any study drug, baseline is defined as the last nonmissing assessment before randomization for all parameters.

When scheduled assessments and unscheduled assessments occur on the same day, and the time of the assessment or time of first dose is not available, use the following convention to determine baseline:

- If both a scheduled and an unscheduled visit are available on the day of the first dose and the time is missing, use the scheduled assessment as baseline.
- If all scheduled assessments are missing on the day of the first dose and an unscheduled assessment is available, use the unscheduled assessment as baseline.

4.1.4. Handling of Missing and Incomplete Dates

In general, values for missing dates will not be handled unless methods for handling missing dates are specified in this section or relevant sections. The original reported dates collected on the eCRF should be used in all relevant listings. The following rules will be used for handling partial dates for analyses requiring dates.

When calculating the time since diagnosis of FL or MZL, a partial diagnosis date will be handled as follows in the calculation:

- If only the day is missing, then the first day of the month will be used.
- If both the month and day are missing, then 01 JAN of the year will be used.
- If the diagnosis date is completely missing, then the time since diagnosis will not be calculated.

When calculating the time between last prior therapy and randomization, a partial last prior therapy date will be handled as described above for diagnosis date.

When the date of the last dose is used in deriving variables such as duration of treatment or TEAE flag, a missing or partial date of the last dose will be handled as follows:

- If only the day is missing, then the earlier date of the last day of the month or the date that the participant discontinued treatment will be used.
- If both the month and day are missing, then the earlier date of 31 DEC of the year or the date that the participant discontinued treatment will be used.
- Otherwise, the date that the participant discontinued treatment will be used as the date of the last dose.

When calculating time to onset or duration of a TEAE, a partial or missing AE onset/end date will be handled in the calculation as follows:

- If only the day is missing, then the first day of the month or Day 1, whichever is later, will be used as the onset date; the earlier date of the last day of the month or the date that the participant withdrew from the study or died will be used as the end date.
- If both the month and day are missing, then 01 JAN or Day 1, whichever is later, will be used as the onset date; the earlier date of 31 DEC or the date that the participant withdrew from the study or died will be used as the end date.
- Otherwise, Day 1 will be used as the onset date, and the missing end date will not be handled.

For relevant efficacy endpoints, a partial date of the death date will be handled as follows in the calculation:

- If mmyyyy for the last known alive date = mmyyyy for the death date, then the death date will be set to the day after the last known alive date.
- If mmyyyy for the last known alive date < mmyyyy for the death date, then the death date will be set to the first day of the death month.
- Otherwise, the partial death date will not be imputed.

4.1.5. Cycle Length and Duration

The scheduled cycle length is 28 days.

Cycle 1 Day 1 is the day that the first dose of study drug (tafasitamab/placebo, lenalidomide, or rituximab) is administered. The actual Day 1 of subsequent cycles will correspond with the first day of administration of tafasitamab/placebo, lenalidomide, or rituximab in that cycle. The date of the Day 1 of subsequent cycles recorded on the eCRF will be used as the Day 1 of the subsequent cycles.

The study consists of the screening period (\leq 28 days), treatment period (up to twelve 28-day cycles for tafasitamab/placebo and lenalidomide, and up to five 28-day cycles for rituximab), and a 5-year follow-up period. The safety follow-up visit (EOT visit) after treatment discontinuation is defined as 90 days after last treatment. The total duration is up to approximately 6 years per participant. The total study duration from FPFV to LPLV is expected to be approximately 8 years.

4.2. Variable Definitions

The following variables will only be calculated if not reported on the eCRF.

4.2.1. Body Surface Area

Body surface area will be calculated based on the Mosteller (1987) formula as follows:

Body surface area (m²) = {[weight (kg) × height (cm)] / 3600} $^{1/2}$.

4.2.2. Prior and Concomitant Medication

Prior medication is defined as any nonstudy medication started before the first dose of tafasitamab/placebo, lenalidomide, or rituximab.

Concomitant medication is defined as any nonstudy medication that is started accordingly:

- Before the date of first administration of tafasitamab/placebo, lenalidomide, or rituximab and is ongoing throughout the study or ends on/after the date of first study drug administration.
- On/after the date of first administration of tafasitamab/placebo, lenalidomide, or rituximab and is ongoing or ends during the course of study.
- If the day of start of administration date is missing, and the first day of the month is on or after the first dose date.
- If the month of start of administration date is missing, and the first day of the year is on or after the first dose date.

A prior medication could also be classified as "both prior and concomitant medication" if the end date is on or after the first dose of tafasitamab/placebo, lenalidomide, or rituximab. In the listing, it will be indicated whether a medication is only prior, only concomitant, or both prior and concomitant.

For the purposes of analysis, all medications will be considered concomitant medications unless the medications can unequivocally be defined as not concomitant.

5. STATISTICAL METHODOLOGY

5.1. General Methodology

Unless otherwise noted, SAS® software (SAS Institute Inc, Cary, NC; v9 or later) will be used for the generation of all tables, graphs, and statistical analyses. Descriptive summaries for continuous variables will include but not be limited to the number of observations, mean, standard deviation, median, minimum, and maximum. Descriptive summaries for categorical variables will include the number and percentage of participants in each category.

Interim analyses are planned for this study as defined in Section 9.

5.2. Treatment Groups

This is a randomized, double-blind, parallel treatment group design. Participants will be summarized by treatment group (see Table 3) for the FL and MZL populations separately and for the overall population.

Table 3: Treatment Groups, Dose Paradigm, and Cycle Length

TGA	TGB
Tafasitamab:	Matching placebo (0.9% saline solution):
12 mg/kg IV on Days 1, 8, 15, and 22 of Cycles 1 to 3 and on Days 1 and 15 (every second week) of Cycles 4 to 12. Cycle length is 28 days.	IV on Days 1, 8, 15, and 22 of Cycles 1 to 3 and on Days 1 and 15 (every second week) of Cycles 4 to 12. Cycle length is 28 days.

Rituximab (including biosimilars):

 $375 \text{ mg/m}^2 \text{ IV}$ every week in Cycle 1 on Days 1, 8, 15, and 22 and on Day 1 of every 28-day cycle from Cycles 2 to 5.

Note: rituximab should be administered approximately 30 minutes after the tafasitamab/placebo infusion is completed. For logistical reasons, rituximab may be administered on the day after the tafasitamab infusion, or administration may be split over 2 consecutive days, according to local practice and the institution's standard of care.

Lenalidomide (including generics):

20 mg PO QD on Days 1 to 21 of every 28-day cycle for 12 cycles.

Note: a participant with moderate renal insufficiency (creatinine clearance ≥ 30 mL/minute to < 60 mL/minute) will receive a starting dose of 10 mg daily on the same schedule. After 2 cycles, if no lenalidomide-related toxicities of Grade 3/4 occur, the dose may be increased to 15 mg QD on Days 1 to 21 of each cycle.

5.3. Analysis Populations

A full description of the populations for analysis is presented in Table 4.

Table 4: Analysis Populations

Population	Description
All screened	All participants who sign the ICF.
FAS	All randomized participants. Treatment groups for this population will be determined according to the treatment they were assigned at the time of randomization.
	The FAS will be used for the summary of demographics, baseline characteristics, participant disposition, and analyses of all efficacy data.
PPS	The subset of the participants in the FAS who are compliant with the requirements of the clinical study Protocol with no important Protocol deviations. All important protocol deviations or conditions leading to exclusion from the PPS will be detailed in the Protocol Deviation Specifications and identified prior to database lock for the primary analysis. Sensitivity analyses of the primary endpoint may be performed using the PPS.
MRD blood-evaluable set	All participants in the FAS who received at least 1 dose of tafasitamab/placebo, lenalidomide, or rituximab with identifiable clonality in blood sample at Cycle 1 Day1.
MRD bone marrow-evaluable set	All participants in the FAS who received at least 1 dose of tafasitamab/placebo, lenalidomide, or rituximab with either identifiable clonality in bone marrow at screening or identifiable clonality in blood sample at Cycle 1 Day 1.
SAF	All randomized participants who received at least 1 dose of tafasitamab/placebo, lenalidomide, or rituximab. Treatment groups for this population will be determined according to the actual treatment the participant received regardless of assigned treatment at the time of randomization. All safety analyses will be conducted using the SAF.
FDG-avid population	All randomized participants with a PET scan at baseline with a resulting Deauville score of 4 or 5.

6. BASELINE, EXPOSURE, AND DISPOSITION

Appendix A provides a list of data displays including the population selected for each analysis (FL, MZL, overall, Japanese FL, Japanese overall). Sample data displays are included in a separate document.

6.1. Demographics, Baseline Characteristics, and Disease History

6.1.1. Demographics and Baseline Characteristics

The following demographics and baseline characteristics will be summarized for the FAS: age, age group (< 65 years), sex (with reproductive status for females and menstrual status for women of childbearing potential), race, ethnicity, geographic region, weight at screening, height at screening, ECOG performance status, and COVID-19 vaccination status at screening.

6.1.2. Baseline Disease Characteristics and Disease History

The following baseline disease characteristics will be summarized for the FAS when applicable to FL or MZL:

- B-symptoms (fever, night sweats, weight loss) at initial diagnosis and at study entry
- Time since initial diagnosis of FL or MZL
- Lymphoma type
- FL grade at initial diagnosis and at study entry
- MZL subtype (splenic, nodal, extranodal)
- Ann Arbor Staging at initial diagnosis and at study entry
- CNS involvement
- FLIPI
- GELF criteria

Bone marrow involvement of disease at baseline and R/R status to the most recent prior therapy will be summarized. Concordance between local and central pathology for FL/MZL diagnosis will also be summarized.

Time since diagnosis will be calculated as follows:

Time since diagnosis (years) = $\frac{\text{date of randomization} - \text{date of diagnosis} + 1}{365.25}$

The following stratification factors per the eCRF will also be summarized: POD24 (yes versus no; FL only), refractoriness to prior anti-CD20 mAb therapy (yes versus no; FL only), and the number of prior lines of therapy ($< 2 \text{ versus} \ge 2$).

6.1.3. Prior Therapy

The number of prior systemic anticancer therapies will be summarized for all participants in the FAS. The component drugs of prior systemic therapies will be coded using the WHO Drug Dictionary. The number and percentage of participants who received each drug will be summarized by WHO drug class and WHO drug PT. The regimen name, purpose of the regimen, best response, reason for discontinuation, date of relapse/progression, medication, start and stop dates, and route will be listed.

The number of prior systemic anti-CD20 immunotherapy and the number of participants who received each regimen will be summarized for all participants in the FAS. The regimen name, purpose of the regimen, best response, reason for discontinuation, date of relapse/progression, medication, start and stop dates, and route will be listed.

The number of participants who received prior radiotherapy will be summarized for the FAS. The anatomical site, start and stop dates, best response, regimen number under the Prior Therapy for Disease CRF (if this oncology radiotherapy is a part of any regimen recorded on the Prior Therapy for Disease under study CRF), number of fractions received, and total dose will be listed.

The number of participants who had prior surgery or a surgical procedure for the malignancies under study will be summarized for the FAS. The date and description of the surgery/procedure will be listed.

The number of participants who had a prior autologous stem cell transplantation might be summarized for the FAS population.

6.1.4. Medical History

For participants in the FAS, medical history will be summarized by assigned treatment group. This summary will include the number and percentage of participants with medical and surgical history event for each body system/organ class as documented on the eCRF. Medical condition/surgery, start date, if it is ongoing at screening, end date, if treated with medication, and worst grade known if ongoing will be listed.

6.2. Disposition of Participant

The number and percentage of participants who were screened, screening disposition and reasons will be summarized for the all screened population. The number and percentage of participants who were randomized, who were treated, who were ongoing with study treatment, who completed study treatment, who discontinued study treatment with a primary reason for discontinuation, who were still in the study, who completed the study, and who withdrew from the study with a primary reason for withdrawal will be summarized for the FAS. The number of participants randomized by country and site will also be provided by treatment group.

6.3. Protocol Deviations

Protocol deviations will be summarized and listed. Important protocol deviations leading to exclusion from the PPS will be identified prior to database lock for the primary analysis and summarized by categories.

6.4. Exposure

For participants in the safety population, exposure to tafasitamab, lenalidomide, and rituximab will be summarized descriptively as follows. Lenalidomide exposure will also be displayed by creatinine clearance group (≥ 30 and < 60 mL/minute vs ≥ 60 mL/minute).

6.4.1. Exposure to Tafasitamab

- **Duration of exposure to tafasitamab (days):** date of last dose of tafasitamab date of first dose of tafasitamab + 1.
- **Duration category of tafasitamab exposure:** the number and percentage of participants in each duration category (ie, < 1 month, 1 to < 3 months, 3 to < 6 months, 6 to < 9 months, 9 to ≤ 12 months, > 12 months) will be summarized. Duration of exposure in month categories will be calculated based on the conversion that each month has 30.4375 days.
- Number of infusions: number of infusions with a nonzero dose.
- Number of cycles: number of cycles with at least 1 nonzero dose infusion.

6.4.2. Exposure to Rituximab

- **Duration of exposure to rituximab (days):** date of last dose of rituximab date of first dose of rituximab + 1.
- **Duration category of rituximab exposure:** the number and percentage of participants in each duration category (ie, < 1 month, 1 to < 3 months, 3 to ≤ 6 months) will be summarized. Duration of exposure in month categories will be calculated based on the conversion that each month has 30.4375 days.
- Number of infusions: number of infusions with a nonzero dose.
- Number of cycles: number of cycles with at least 1 nonzero dose infusion.

6.4.3. Exposure to Lenalidomide

- **Duration of treatment with lenalidomide (days)**: date of last dose of lenalidomide date of first dose of lenalidomide + 1.
- **Duration category of lenalidomide exposure:** the number and percentage of participants in each duration category (ie, < 1 month, 1 to < 3 months, 3 to < 6 months, 6 to < 9 months, 9 to ≤ 12 months, > 12 months) will be summarized. Duration of exposure in month categories will be calculated based on the conversion that each month has 30.4375 days.
- Total dose received (mg): the sum of the cumulative actual dose of lenalidomide that has been taken by the participant.

6.5. Dose Intensity, Relative Dose Intensity

For participants in the safety population, the actual dose intensity and relative dose intensity of tafasitamab, lenalidomide, and rituximab will be summarized descriptively. The actual or planned dose intensity will be calculated by summing up the visit-wise actual or planned doses.

6.5.1. Dose Intensity and Relative Dose Intensity of Tafasitamab

Actual dose intensity (mg/kg): the actual dose the participant was exposed to. The ADI per infusion will be derived as follows:

- If the question "was the entire infusion administered" on the "Tafasitamab/Placebo Infusion" eCRF page was answered with
 - Yes

ADI at the visit = 12 mg/kg

No

ADI at the visit = 12 mg/kg (actual volume administered / prepared volume)

- Skipped doses will result in an ADI of 0 for the particular visit.
- The ADI will be calculated by summing up all infusion-wise actual doses.

Planned dose intensity (mg/kg): The planned dose is 12 mg/kg per infusion as per Protocol.

Relative dose intensity (%): The RDI expresses the amount of drug administered compared with the planned amount of drug across all infusions.

 $RDI = ADI / (PDI \times the number of infusions) \times 100$

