6.4. Study Treatment Compliance

Compliance with study treatment administration will be calculated by the sponsor based on study drug accountability and infusion records documented by the site staff and monitored by the sponsor/designee.

Participants should receive tafasitamab/placebo under direct supervision of clinical study site unblinded personnel. Each administration volume will be checked, and the vial code and volume per administration will be recorded in each participant's eCRF as well as in the source data. Unblinded data for tafasitamab will be captured in a separate eCRF database via the IRT system and will be monitored by an unblinded CRA. Refer to the Pharmacy Manual and Suvoda IRT Site User Manual for details.

The dosing of tafasitamab or placebo will be considered appropriate if the dose administered is $\geq 80\%$ to $\leq 120\%$ of the assigned dose per single infusion. Overdose treatment is described in Section 9.10.

Lenalidomide will be dispensed on Day 1 of each new treatment cycle. Participants will return all unused or empty lenalidomide blister packs to the clinical study site throughout the treatment period as instructed by the investigator, and keep a record of lenalidomide doses taken at home, which will be reviewed by clinical study site personnel on an ongoing basis. The clinical site personnel will document the amount of study drug received from and returned to the sponsor and dispensed to participants in accordance with local regulatory requirements. Throughout the course of the study, drug accountability records must be maintained. A participant will be considered compliant with the Protocol if the lenalidomide dose administered is $\geq 80\%$ to 100% of the assigned dosage. Overdose treatment is described in Section 9.10.

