9.10. Treatment of Overdose

The sponsor is not recommending any specific treatment of a suspected overdose of tafasitamab, rituximab, and/or lenalidomide. In case an overdose of tafasitamab, rituximab, and/or lenalidomide happens and requires treatment, symptomatic treatment including but not limited to blood product transfusions, growth factors, antibiotics, antiemetics, and analgesics may be administered per investigator's discretion.

For purposes of this study, overdose of tafasitamab/rituximab is defined as any tafasitamab/rituximab dose above 120% of the assigned dosage per single infusion as per Protocol.

For lenalidomide the overdose is defined as any dose greater than the planned dose for a particular participant as per Protocol.

Overdose is not an SAE unless it meets the criteria of an SAE (see Section 9.2).

In the event of an overdose, the investigator should do the following:

• Contact the medical monitor immediately.

- Closely monitor the participant for any AE/SAE and laboratory abnormalities as clinically appropriate.
- Document the quantity of the excess dose as well as the duration of the overdose in the eCRF.

Decisions regarding dose interruptions or modifications will be made by the investigator in consultation with the medical monitor based on the clinical evaluation of the participant.

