6.5.2. Dose Intensity and Relative Dose Intensity of Rituximab

Actual dose intensity (mg/m²): the actual dose to which the participant was exposed. The ADI per infusion will be derived as follows:

- If the question regarding whether the participant was given the protocol standard 375 mg/m² dose was answered with
 - Yes

Actual rituximab dose level $(mg/m^2) = 375 \text{ mg/m}^2$

- No

Actual rituximab dose level (mg/m^2) = total prepared dose (mg) / participant BSA (m^2) on Day 1 of the cycle

- If the question "was the entire infusion administered" on the "Rituximab Infusion" eCRF page answered with
 - Yes

ADI at the visit = actual rituximab dose level (mg/m^2)

- No

ADI at the visit = actual rituximab dose level $(mg/m^2) \times (actual volume administered / planned volume)$

- Skipped doses will result in an ADI of 0 for the particular visit.
- The ADI will be calculated by summing up all infusion-wise actual doses.

Planned dose intensity (mg/m²): The planned dose is 375 mg/m² as per Protocol.

Relative dose intensity (%): The RDI expresses the amount of drug administered compared with the planned amount of drug across all infusions.

 $RDI = ADI / (PDI \times the number of infusions) \times 100$

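### Tafasitamab dose intensity in SAP 6.5.1 is the nominal 12 mg/kg times the fraction of the bag infused, so it cannot show preparation or weight errors or any dose above 120%, and no planned summary reports the Protocol's 80–120% criterion

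*SAP*

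**What the plan says.** SAP 6.5.1 has two branches. If the eCRF records that the whole infusion was given, "ADI at the visit = 12 mg/kg". If not, "ADI at the visit = 12 mg/kg (actual volume administered / prepared volume" (12 multiplied by the volume ratio). A skipped dose counts as 0. The reference value is also fixed: "The planned dose is 12 mg/kg per infusion as per Protocol". RDI is total ADI over planned dose times number of infusions.

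The Protocol treats the delivered dose as something that can vary:
- Section 6.1 bases tafasitamab dosing on the weight from the most recent cycle.
- Section 6.4 sets a per-infusion criterion: "The dosing of tafasitamab or placebo will be considered appropriate if the dose administered is" at least 80% and at most 120% of the dose assigned.
- Section 9.10 adds that "overdose of tafasitamab/rituximab is defined as any tafasitamab/rituximab dose above 120% of the assigned dosage per single infusion".

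Protocol 6.4 also states that "Compliance with study treatment administration will be calculated by the sponsor based on study drug accountability and infusion records". The SAP has one compliance section, 6.6, and it covers lenalidomide only. Appendix A of the SAP has exposure tables and dosing listings for tafasitamab, but no table of infusions against the 80–120% range.

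The other two drugs are handled differently. For rituximab, SAP 6.5.2 uses "total prepared dose (mg) / participant BSA" when the standard dose was not given. For lenalidomide, SAP 6.5.3 uses the dose recorded in the eCRF.

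**The concern.** A variable introduced as the dose actually received contains no received dose. A bag made up with too little or too much drug, or made up for an outdated weight, counts as exactly 12 mg/kg once it has been infused in full. These are errors that an 80–120% rule is suited to detect. An infusion documented as an overdose under Protocol 9.10 would still contribute 100% to RDI.

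At stake is the description of exposure to the investigational drug, which is the background for reading the safety comparison. As written, tafasitamab RDI is partly fixed by construction rather than measured.

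**Working it through.** The plan states no figure to reproduce. The check applies the SAP 6.5.1 rule to assumed cases and compares the result with the dose given.

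**Inputs from the documents**
- Planned dose 12 mg/kg per infusion (SAP 6.5.1).
- Limits 80% and 120% per infusion (Protocol 6.4): 0.8 × 12 = 9.6 mg/kg and 1.2 × 12 = 14.4 mg/kg.
- Schedule (Protocol 6.1): 3 cycles × 4 + 9 cycles × 2 = 30 infusions.
- Reconstituted strength 40 mg/mL; 200 mg per vial (Protocol 6.2.1).

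**Formulas**
- SAP rule: 12 if complete, otherwise 12 × (administered volume / prepared volume).
- Dose given: (prepared mg / weight) × (administered volume / prepared volume).

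**Assumed cases, bag infused in full**

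| Prepared, as % of assigned | Dose given (mg/kg) | SAP ADI (mg/kg) | SAP % |
|---|---|---|---|
| 50 | 6.0 | 12 | 100 |
| 70 | 8.4 | 12 | 100 |
| 130 | 15.6 | 12 | 100 |
| 150 | 18.0 | 12 | 100 |

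In milligrams, again assumed:
- 800 mg to an 85 kg participant: 800 / 85 = 9.4 mg/kg, and 9.41 / 12 = 78%. This is below the limit; the SAP scores 100%.
- 1200 mg prepared for an old weight of 100 kg and given at 80 kg: 1200 / 80 = 15.0 mg/kg, and 15 / 12 = 125%. This is an overdose under Protocol 9.10; the SAP scores 100%.

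**Assumed cases, bag not finished**
- Prepared correctly, 79% of volume infused: true 79%, SAP 79%. Here the lower limit is visible.
- Prepared at 70%, 90% infused: 0.70 × 0.90 = 63% true; SAP 90%.
- Prepared at 130%, 70% infused: 1.30 × 0.70 = 91% true; SAP 70%.
- Prepared at 130%, 95% infused: 1.30 × 0.95 = 123.5% true; SAP 95%.

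The administered volume cannot exceed the prepared volume, so the SAP percentage for one infusion cannot exceed 100%. No breach of the upper limit can appear, whether or not the bag was finished.

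**Effect over a full course.** One bag of 30 prepared at 130%, the rest correct and all infused in full: (29 + 1.3) / 30 = 101.0% true, against 100% under the SAP. A single error barely moves course RDI. What is lost is mainly the per-infusion count and any systematic error.

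**The case against.** The best defence is that nominal dose times fraction infused is a reasonable simplification. Tafasitamab dose reductions are not permitted (Protocol 6.5.1, SAP 6.7), so 12 mg/kg is the only assigned level, and the rule works identically in both arms. Protocol 10.4.2 promises only descriptive exposure measures, and Protocol 6.4 does not say the 80–120% criterion will be tabulated. Weight is measured on Day 1 of each cycle, so large weight errors should be uncommon.

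Part of this stands. Comparability between arms is a good reason to keep the present measure, and the examples above are illustrations, not observed errors. But a bar on planned reductions does not prevent preparation errors, and a measure of bag completion should not be presented as the dose received.

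A reader might infer more than the documents support:
- *That the 80–120% limits can never be assessed.* Unfinished infusions can show below 80%. Protocol 6.4 records vial code and volume per administration and keeps unblinded tafasitamab data in a separate database, Protocol 6.2.3 keeps vial counts, and Protocol 9.10 has the excess quantity of an overdose entered in the eCRF. SAP Appendix A plans tafasitamab dosing listings. The information is collected; the planned summaries do not use it.
- *That the SAP credits nominal dose for all three drugs.* It does not for lenalidomide, nor for rituximab when the standard dose was not given.
- *That split rituximab doses are counted twice.* SAP Table 3 says "administration may be split over 2 consecutive days, according to local practice", and no rule combines the parts. Double crediting would need two eCRF records per dose and, for each part, a Yes to having received the standard 375 mg/m². The eCRF layout is not in the documents. If each part is entered with its own prepared dose, the two sum correctly. This is not shown to be an error.

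**Conclusion.** The point holds for tafasitamab. Every fully infused bag scores 100% whatever was prepared, no infusion can score above 100%, and the share below 80% is understated to the extent that under-prepared bags are finished. No planned SAP summary reports the Protocol 6.4 criterion, and the SAP plans no tafasitamab compliance analysis.

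The consequence is limited to descriptive exposure summaries. Efficacy estimates, tests and type I error do not depend on ADI or RDI. The actual size cannot be given, because the documents contain no frequency of preparation or weight errors; the percentages in the check rest on assumed errors. The conclusion itself rests only on the SAP formula and on administered volume not exceeding prepared volume.

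**What to change.** 1. In SAP 6.5.1, keep the present measure for both arms but label it as the fraction of the prepared infusion delivered. The arms then stay comparable.
2. For the tafasitamab arm, after unblinding, add ADI = (prepared mg / weight at the most recent cycle) × (administered volume / prepared volume), with the matching RDI.
3. Take prepared mg from the unblinded dosing records as reconstituted volume used × 40 mg/mL. Vial count × 200 mg will not do, because it ignores partly used vials. A correct dose at 52 kg is 52 × 12 = 624 mg and needs 4 vials; counted as 800 mg it reads 800 / 52 = 15.4 mg/kg, or 128%, a false overdose. First confirm that the unblinded records hold the reconstituted volume or the milligrams used, since the Protocol mentions only vial code, vial counts and volume per administration.
4. Add one table to Appendix A: number and percentage of tafasitamab infusions below 80%, within 80–120% and above 120% of the assigned dose.

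The cost is SAP wording, programming and a merge of the unblinded dosing data at the primary analysis, when the blind ends under Protocol 6.3. The resulting RDI may look slightly less favourable than the present one.
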